#### **Biochemistry**

- Alkaline phosphatase (AP),
- Alanine aminotransferase (ALT),
- Aspartate aminotransferase (AST),
- Gamma Glutamyl Transferase (γ-GT),
- Blood urea nitrogen (BUN),
- Serum bilirubin,
- Serum creatinine,
- Sodium,
- Potassium,
- Chloride,

Final Version 5.0 Page 64 of 76

- Bicarbonate,
- Calcium,
- Magnesium.

Descriptive statistics of observed values and changes from baseline will be presented by visit and treatment group. The summaries described in this section will be presented relative to baseline, defined as the most recent, non-missing result on or before the date of randomization. No imputation for missing data will be performed.

All clinical laboratory data reported in the eCRF will be presented in by-patient listings.

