### 15 STATISTICS

This section presents an overview of the planned analyses. Final analyses are not limited to the summaries described herein. The Statistical Analysis Plan (SAP) will provide a detailed description of the planned statistical analyses and data summaries. If circumstances arise during the clinical trial that make these analyses inappropriate or if improved methods become available, the SAP may be revised. If discrepancies exist between the text of the statistical analysis as planned in the protocol and the final SAP, the final SAP will define the planned analysis of record. Reasons for such discrepancies will be described in the final Clinical Study Report (CSR).

This is a Phase III, prospective, multicenter, randomized, controlled trial with one blinded, adaptive interim analysis for sample size re-estimation and final identification of the model to be used for the primary analysis.

The primary outcome measure of the trial is the difference in mean FEV1 (mL) change from baseline to Week 48 between the L-CsA plus SoC and SoC alone groups CCI

For the purpose of this study, "baseline  $FEV_1$ " is the mean of the best  $FEV_1$  obtained at the Screening Visit and the best  $FEV_1$  obtained at the Baseline (randomization) Visit.

For all spirometer-based measurements see Section 12.1.1.

Data will be listed by patient and treatment group.

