#### 15.2.5.3 Laboratory and Other Safety Evaluations

For clinical safety laboratory test results and vital signs, the numeric values and corresponding changes from baseline will be summarized using descriptive statistics by parameter and time point. In addition to the tables showing the distribution parameters, laboratory measures will be presented in 'shift tables' that show the position of all patients relative to the applicable reference range at clinical trial entry, broken down by the position at clinical trial exit. Common Toxicity Criteria (CTC version 5.0) will be applied to abnormal laboratory test results and abnormal vital signs.

Parameters reflecting acute tolerability of IMP (spirometry, cough, or dyspnea) will be summarized.

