#### 8 STATISTICAL CONSIDERATIONS

### 8.1 General Considerations and Descriptive Statistics

All report outputs will be produced using version 9.2 or later, in a secure and validated environment. All tables, figures and data listings (TFLs) to be included in the report will be independently checked for consistency and integrity.

The data recorded in the eCRF will be summarized as appropriate, per treatment group and for the total group, using the following descriptive measures:

- All continuous variables will be summarized using descriptive statistics (i.e., n, mean, standard deviation (SD), median, Q1, Q3, minimum, and maximum).
- All categorical variables will be summarized by using frequency counts and percentages.
- Discrete ordinal or higher-level data will be summarized as continuous data, but a tabulation of categories may also be included, depending on the number of categories.
- For time-to-event variables, cumulative event-free survival times will be evaluated using
  the Kaplan-Meier method. A frequency table showing the number of events and censored
  patients by treatment group, will be presented along with the event-free rates (and twosided 95% confidence). Kaplan-Meier graphs will be presented along with the number of
  patient-at-risk at exact time points. If different rules are not specified, patients who are free
  from event will be censored at the study termination.

For all measures analyzed descriptively (i.e., measures to characterize the treatment groups and their baseline status, efficacy, and safety outcomes), tabulations comparing the treatment groups will be prepared. For outcomes measured more than once, the analyses will include tabulations of the measured values by visit, as well as change from baseline. Where provided, all confidence intervals will be two-sided 95% intervals.

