#### 15.6 Renal Function

In addition to the summarization of serum creatinine as described in previous section, renal dysfunction will be further listed and summarized by treatment group based upon the classification of AEs with the following PTs (see protocol section 13.1.5.4, Table 7):

- Blood Creatinine Increased;
- Renal Impairment;
- Renal Failure.

Final Version 5.0 Page 65 of 76

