### 15.7 Vital Signs

Vital signs will be assessed at each visit. The following vital signs will be recorded:

- Systolic and diastolic blood pressure (sitting, after 5 minutes of rest);
- Heart rate (sitting, after 5 minutes of rest);
- Body temperature (the same method should be used for each patient and throughout the trial);
- Respiratory rate;
- Weight.

The summaries described in this section will be presented relative to baseline, defined as the most recent, non-missing result on or before the date of randomization. No imputation for missing data will be performed.

Descriptive statistics of observed values and for changes from baseline will be presented by visit and treatment group on SAF. Vital signs data reported in the eCRF will be presented in by-patient listings.

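### The governing SAP leaves out the Protocol's laboratory shift tables and CTC grading, so no table counts by arm the patients whose creatinine or other value crosses a limit or grade

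*SAP*

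**What the plan says.** Protocol 15.2.5.3 plans more than summary statistics. It states that "laboratory measures will be presented in 'shift tables' that show the position of all patients relative to the applicable reference range", with position at entry cross-classified by position at exit. It also states that "Common Toxicity Criteria (CTC version 5.0) will be applied to abnormal laboratory test results and abnormal vital signs". Protocol 13.1.6 repeats the grading for vital signs. Where Protocol and SAP differ, Protocol section 15 says that "the final SAP will define the planned analysis of record".

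For haematology and biochemistry, SAP 15.5.1 plans this: "Descriptive statistics of observed values and changes from baseline will be presented by visit and treatment group". It adds a by-patient listing of all laboratory data. SAP 8.1 defines descriptive statistics for continuous variables as "n, mean, standard deviation (SD), median, Q1, Q3, minimum, and maximum". For vital signs, SAP 15.7 reads "Descriptive statistics of observed values and for changes from baseline will be presented by visit and treatment group on SAF", again with listings. For renal function, SAP 15.6 keeps the creatinine summary and adds a listing and summary by arm "based upon the classification of AEs with the following PTs", naming three preferred terms and citing Protocol Table 7.

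In the readable SAP text, CTC occurs only in the abbreviation list, and a laboratory shift table occurs nowhere. The readable entries of SAP section 16 (changes from planned analyses) mention neither. Several entries there are redacted.

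**The concern.** Renal function is a named safety endpoint (Protocol 9.1, SAP 7.6), Protocol 13.1.5.4 singles out serum creatinine, and the product is a calcineurin inhibitor added to systemic tacrolimus. A safety signal in laboratory data is often a handful of patients with large changes rather than a shift of the whole arm. Shift tables and grade tables turn such patients into a number per arm that can be compared. Without them, the report would hold by-visit distributions, raw listings and AE tables, and a reader would have to go through the listings by hand to learn how many patients in each arm crossed a limit. Because the SAP is the analysis of record, the Protocol's commitment does not by itself bring the tables back.

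**Working it through.** The plan states no figure on this point, so there is none to reproduce. The check is a comparison of the two documents, followed by a small illustration.

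**1. Side by side**

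| Output | Protocol | SAP (readable text) |
|---|---|---|
| Values and changes by visit | 15.2.5.3 | 15.5.1, 15.7; content defined in 8.1 |
| Entry-by-exit position against reference range (laboratory) | 15.2.5.3 | none |
| CTC v5.0 grade | 15.2.5.3 (laboratory, vital signs), 13.1.6 (vital signs) | none |
| Individual values | listings (section 15) | listings (15.5.1, 15.7) |
| Renal AEs | terminology in Table 7 | three preferred terms (15.6), plus all TEAEs (15.3) |

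The second and third rows are the only outputs that would count patients by laboratory value. Both are missing from the SAP.

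**2. What the by-visit statistics show**

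Inputs: 169 randomized (SAP 8.2) at 1:1, so 169/2 = 84.5, taken as 85 per arm. The documents give neither a creatinine SD nor an event rate. The number of affected patients k, the rise r and the SD are therefore assumptions.

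Shift in the arm mean = k × r / 85:
- 1 patient, 1.0 mg/dL: 1 × 1.0 / 85 = 0.012 mg/dL
- 3 patients, 1.5 mg/dL: 3 × 1.5 / 85 = 0.053 mg/dL
- 5 patients, 2.0 mg/dL: 5 × 2.0 / 85 = 0.118 mg/dL

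The quartiles and the maximum were checked by simulation: 5,000 arms of 85, normal changes with mean zero, and three patients raised by 1.5 mg/dL.

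| Assumed SD of change (mg/dL) | Movement of Q3 | Maximum without the rises | Maximum with the rises |
|---|---|---|---|
| 0.1 | 0.009 | 0.24 | 1.58 |
| 0.2 | 0.017 | 0.49 | 1.67 |
| 0.3 | 0.026 | 0.74 | 1.75 |

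So the mean and Q3 hardly move, while the maximum moves clearly. The maximum does not count, however. If every affected patient changes by exactly 1.5 mg/dL and nobody else changes by more, it is 1.5 whether one patient (1/85 = 1.2%) or five (5/85 = 5.9%) are affected.

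**3. What the windowing rule can remove**

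SAP 9.4 assigns scheduled and unscheduled measurements to visit windows. Where a window holds several, it uses the one closest to the scheduled time, unless an additional one is the patient's last in the trial. Take the Visit 6 window (141 to 196 days, nominal day 169), a scheduled sample at 168 days and an unscheduled peak at 185 days. The scheduled sample is closer, so the peak leaves the by-visit summary, including its maximum, and stays only in the listing.

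**4. What the AE route captures**

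Under Protocol 13.1.1.1 an abnormal result becomes an AE only if it points to a clinical condition that qualifies as one. That is a judgement, and Protocol 9.3.1 leaves treating physicians and study staff unblinded. Table 7 also gives renal impairment, acute renal dysfunction and severe renal dysfunction the same preferred term. A count of that term therefore does not separate a temporary rise from a stable value above 2.5 mg/dL. The severity and seriousness tables in SAP 15.3 separate them only in part.

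**The case against.** The case against is substantial, and it limits the point. A reader might infer three stronger things that the documents do not support.

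- *That renal safety is reported only as group means.* SAP 8.1 includes quartiles, minimum and maximum, and SAP 15.5.1 lists every laboratory value by patient.
- *That affected patients would not show.* In the illustration the visit maximum more than doubles at every assumed SD, and each patient is in the listings. The DMC also sees serum creatinine by arm (SAP 8.5). What is missing is the count.
- *That renal AEs under other terms go uncounted.* SAP 15.3 tabulates all TEAEs by system organ class and preferred term, with severity, relationship and seriousness. SAP 15.6 adds to those tables, and its three terms come from Protocol Table 7, so they are not an arbitrary narrowing by the SAP.

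It would also go too far to say that the omission is undisclosed or deliberate. Section 16 has redacted entries, SAP 9.1 refers to table shells that are not in the public documents, and the surviving abbreviation fits a drafting slip.

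Finally, the Protocol's shift table compares entry with exit. A rise that resolves before exit would not appear in it, and a patient above range at both times would show no shift. Restoring it alone would not count every crossing, and a worst post-baseline summary is an addition to the Protocol's plan.

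All of this stands. None of it supplies a count per arm of patients crossing a laboratory limit or grade.

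**Conclusion.** The point holds in a limited form. Two outputs planned in Protocol 15.2.5.3 are absent from the readable text of the governing SAP, with no readable explanation. As written, a patient whose creatinine or other laboratory value crosses a limit or grade can be found only through a visit minimum or maximum, in a listing, or through an AE that an unblinded investigator chose to report. A peak at an unscheduled visit may be missing from the by-visit summaries altogether. The CTC grading of vital signs is lost in the same way.

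The size is modest: a gap in safety tabulation, with no effect on the efficacy analysis or on trial conduct. The text comparison assumes that neither the redacted entries nor the unseen table shells restore the tables. The mean shifts of 0.012 to 0.118 mg/dL rest on assumed rises in 1 to 5 patients and are no forecast of what the trial will show.

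**What to change.** - In SAP 15.5.1, restore the Protocol's entry-to-exit shift tables by arm, using each local laboratory's reference range, and the counts of patients by CTC v5.0 grade. In 15.7, restore the CTC v5.0 grade counts for vital signs.
- Add the worst post-baseline grade per patient, taken over all scheduled and unscheduled values before the windowing in SAP 9.4.
- In SAP 15.6, add a count by arm of patients with any post-baseline creatinine above 2.5 mg/dL, the level already used in Protocol Table 7. This is for tabulation only and implies nothing about patient management. Exclusion criterion 10 bars values above that level at screening, so nearly all such values would be new crossings.
- If the sponsor prefers to leave the planned tables out, say so and give the reason in SAP section 16.

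The cost is a few extra tables from data already collected. It assumes that the local reference ranges are held with the results, which the Protocol's own shift tables require. Visits, sampling and the error-rate plan are unchanged.

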### 15.5.2 Blood Sampling CNI/mTOR Inhibitors

A whole blood sample for the determination of blood sampling CNI/mTOR inhibitors will be collected at each visit; this includes cyclosporine A and/or tacrolimus trough level. In patients allocated to L-CsA plus SoC, the sample should be collected 60 min before L-CsA inhalation. Blood samples will be evaluated by the local laboratories associated with each site. The summaries described in this section will be presented relative to baseline, defined as the most recent, non-missing result on or before the date of randomization. No imputation for missing data will be performed.

All CNI/mTOR data reported in the eCRF will be presented in by-patient listings. Descriptive statistics of observed values and changes from baseline will be presented by visit and treatment group.

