#### 9.2 Trial Design

This is a Phase III, prospective, multi-center, randomized, controlled clinical trial in the treatment of BOS in adult recipients of a bilateral pulmonary allograft. Approximately 160-170 patients are planned for enrollment. The clinical trial will be conducted in approximately 43 centers worldwide. Patients will be randomly allocated to receive either L-CsA plus SoC or SoC alone for the treatment of BOS. Patients will be monitored every 4-8 weeks over 48 weeks for efficacy parameters and for all safety evaluations.

The rationale for not using a placebo control is driven by concerns that a sucrose-containing formulation could increase a potential risk of pulmonary infection without the benefit of L-CsA. Sucrose is a lyoprotectant in the manufacturing process. After carefully weighing alternative options for lyoprotection, no sugar-free alternatives that qualify as real placebo (i.e., undistinguishable by means of appearance, taste or smell) could be identified. Therefore, a randomized controlled trial versus SoC is the only suitable alternative.

An open-label clinical trial generally bears the potential regarding biased patient treatment and care, and thus trial outcome. However, for this trial the risk of bias is considered low because of the following reasons:

- Currently, the general strategy to treat BOS is augmentation of immunosuppressive therapy
  to the highest tolerable level unless limited by systemic toxicity. Since application of L-CsA
  via inhalation has not shown to lead to an additional systemic drug burden, dose reductions or
  adaptations of other components of the immunosuppressive cocktail will not be required and
  are not desired.
- Furthermore, the selected primary endpoint FEV1 is an objective parameter and its measurement will be performed according to recommended guidelines of ATS/ERS which have to be respected by each participating center. Following this methodology, a subjective and intentional manipulation of outcome is highly unlikely even if health care professional and patient are aware of the treatment allocation.
- The pulmonary function technicians, respiratory therapists, or physiotherapists who perform spirometry at each site will be blinded to each study patient's study treatment assignment.

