#### 11.3.4 Other Medication

All concurrent treatment or medications given within 30 days prior to Randomization and until Visit 10/EoS, will be recorded in the CRF.

The use of any inhaled formulation of Cyclosporine A other than the IMP is strictly prohibited during the complete clinical trial period. Topical formulations (e.g., eye drops) containing CsA are allowed. Patients should not receive systemic Cyclosporine A at any time during Screening and Randomization. If medically indicated after Randomization, the treating physician can exchange Tacrolimus for systemic Cyclosporine A.

All inhaled medications, except investigational inhaled medications, are permissible during the trial and should be administered in the following order: inhaled bronchodilators, inhaled corticosteroids, inhaled antifungals/antibiotics, and then inhaled L-CsA. Spirometry must be performed without the use of bronchodilators (see Section 12.1.1.1) and preferably before but at least 2 hours after the last administration of inhaled antifungals/antibiotics.

To standardize spirometry across the two treatment arms, patients should not use short-acting bronchodilators (e.g., albuterol) 2 hours prior to spirometry. Patients on scheduled Long-Acting Beta Agonists (LABAs) or Long-Acting Muscarinic Antagonists (LAMAs) should ideally have spirometry done at the same time of day following their scheduled dose. Patients have to note their use and timing of bronchodilators carefully.

Protocol Number:

Sponsor:

L-CsA:

The reason for non-compliance shall be documented accordingly on the respective CRF.

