#### 13.1.5.2 Cyclosporine A and Tacrolimus Whole Blood Trough Levels

A whole blood sample for the determination of cyclosporine A and/or tacrolimus trough level will be collected at each visit. In patients allocated to L-CsA inhalation, the sample should be collected within 60 minutes before inhalation. The mean cyclosporine A and/or tacrolimus trough level will be compared across treatment groups. Blood samples will be evaluated by the local laboratories.

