#### 26 APPENDIX II – ACCEPTABLE METHODS OF CONTRACEPTION

A woman is considered of childbearing potential, i.e. fertile, following menarche and until becoming post-menopausal unless permanently sterile. The status of post-menopausal is defined as no menses for 12 months without an alternative medical cause and/or the age of 60 years.

According to the Clinical Trial Facilitation Group (CTFG) dated 15/04/2014, the following methods are allowed for contraception during the clinical trial with a failure rate of less than 1%:

- combined (estrogen and progestogen containing) hormonal contraception associated with inhibition of ovulation:
  - o oral
  - o intravaginal o transdermal
- progestogen-only hormonal contraception associated with inhibition of ovulation 1:
  - o oral
  - o injectable
  - o implantable
- intrauterine device (IUD)
- intrauterine hormone-releasing system (IUS)
- bilateral tubal occlusion
- vasectomised partner
- sexual abstinence

From results of previous clinical trials with aerosolized L-CsA potential interactions between the IMP and hormonal contraceptives have not been investigated. It is recognized that hormonal contraceptives can increase serum levels of systemically dosed cyclosporine, but cyclosporine does not alter the efficacy of hormonal contraceptives. Subjects in the trial will be monitored for systemic cyclosporine levels.

<sup>1 Hormonal contraception may be susceptible to interaction with the IMP, which may reduce the efficacy of the contraception method

<sup>2 Contraception methods that in the context of this guidance are considered to have low user dependency.

<sup>3Vasectomised partner is a highly effective birth control method provided that partner is the sole sexual partner of the WOCBP trial participant and that the vasectomised partner has received medical assessment of the surgical success.

<sup>4 In the context of this guidance sexual abstinence is considered a highly effective method only if defined as refraining from heterosexual intercourse during the entire period of risk associated with the study treatments. The reliability of sexual abstinence needs to be evaluated in relation to the duration of the clinical trial and the preferred and usual lifestyle of the subject.

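### Cyclosporine A trough levels are summarised by arm without separating samples taken after a permitted switch to systemic cyclosporine, so a small imbalance in switches can distort or reverse the comparison of means.

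*SAP*

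**What the plan says.** Protocol 11.3.4 sets the rule on systemic CsA. Before treatment starts: "Patients should not receive systemic Cyclosporine A at any time during Screening and Randomization". Later: "If medically indicated after Randomization, the treating physician can exchange Tacrolimus for systemic Cyclosporine A". The permission is not limited to one arm.

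Protocol 13.1.5.2 covers sampling and comparison: "A whole blood sample for the determination of cyclosporine A and/or tacrolimus trough level will be collected at each visit", and "The mean cyclosporine A and/or tacrolimus trough level will be compared across treatment groups". SAP 15.5.2 carries this out by visit and arm: "Descriptive statistics of observed values and changes from baseline will be presented by visit and treatment group". It takes baseline as the latest non-missing result up to the day of randomization, imputes nothing, and lists all levels by patient.

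The SAP expects systemic CsA to occur: section 12.1 names it with tacrolimus in the calcineurin-inhibitor class. Section 12 identifies immunosuppressants by drug code and route. No legible section uses that information to split, exclude or flag blood levels, and the subgroup section (14.6) covers efficacy variables only.

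**The concern.** A CsA level in this trial can come from two sources: absorption of inhaled L-CsA, or systemic CsA started after randomization. Control patients are not assigned L-CsA and may not use any other inhaled CsA, so a measurable level there would normally mean a switch. A summary by arm alone adds the two sources together, and systemic dosing can be expected to give much the higher level.

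This matters because the protocol leans on low systemic exposure. Section 7.1.3 describes the rise in calcineurin-inhibitor levels seen so far as negligible. Section 9.2, in arguing that the risk of open-label bias is low, says that L-CsA "via inhalation has not shown to lead to an additional systemic drug burden". Appendix II adds: "Subjects in the trial will be monitored for systemic cyclosporine levels". The troughs are the only blood CsA measurements in the legible documents, so a reader will naturally turn to this table to see whether the premise held over 48 weeks.

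**Working it through.** The documents state no CsA level, switch rate or precision, so there is no plan figure to reproduce. What follows is an illustration on assumed levels.

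**Inputs**
- Patients: 169 randomized (SAP 8.2). At 1:1, take 85 on L-CsA and 84 on standard of care (SoC). This split is assumed, and drop-out is ignored.
- Inhaled-only trough *i*: assumed 2 to 20 ng/mL.
- Systemic trough *s*: assumed 100 to 250 ng/mL.
- Switched patients: *kL* on L-CsA, *kS* on SoC. A switched L-CsA patient is taken to keep inhaling.

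**Case 1: every patient assayed, with zero for unswitched SoC patients**

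L-CsA mean = *i* + *kL* × *s* / 85. SoC mean = *kS* × *s* / 84.

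With *i* = 5 and *s* = 150 (ng/mL):

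| *kL* | *kS* | L-CsA mean | SoC mean | Difference |
|---|---|---|---|---|
| 0 | 0 | 5.0 | 0.0 | +5.0 |
| 2 | 2 | 8.5 | 3.6 | +5.0 |
| 5 | 5 | 13.8 | 8.9 | +4.9 |
| 5 | 2 | 13.8 | 3.6 | +10.3 |
| 2 | 5 | 8.5 | 8.9 | −0.4 |
| 2 | 8 | 8.5 | 14.3 | −5.8 |

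The difference attributable to inhalation is +5.0 in every row. Balanced switching raises both means but leaves the difference nearly unchanged. Imbalance doubles it or changes its sign. The medians are 5 and 0 in every row.

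**Reversal threshold.** With no switches on L-CsA, the SoC mean is the higher once *kS* > 84 × *i* / *s*. Smallest whole *kS*:

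| *i* | *s* = 100 | *s* = 150 | *s* = 250 |
|---|---|---|---|
| 2 | 2 | 2 | 1 |
| 5 | 5 | 3 | 2 |
| 10 | 9 | 6 | 4 |
| 20 | 17 | 12 | 7 |

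The range is 1 of 84 (1.2%) to 17 of 84 (20%).

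**Share of the L-CsA mean due to switched patients** = *kL* × *s* / (85 × *i* + *kL* × *s*). With *i* = 5 and *s* = 150:
- one switch: 150/575 = 26%
- two switches: 300/725 = 41%
- three switches: 450/875 = 51%

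So systemic dosing supplies most of the mean from the third switch on. With *i* = 10 it takes six: 900/1750 = 51%.

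**Case 2: SoC patients assayed for CsA only while taking it**

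One switched SoC patient then gives a SoC mean and median of 150, against an L-CsA mean of 5.0 to 13.8 in the scenarios above. The and/or wording in Protocol 13.1.5.2 does not say which case applies.

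**With the split.** Among samples with no systemic CsA, Case 1 gives 5.0 on L-CsA and 0.0 on SoC, however many patients switch.

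**The case against.** The case against has several sound parts.

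- **Switching should be uncommon.** Protocol 11.3.1 asks sites to keep the type of immunosuppressive drug unchanged, and Protocol 11.3.4 allows the exchange only on medical grounds. With one or two switches, or equal numbers per arm, the means do little harm.
- **Other output limits the damage.** SAP 8.1 requires n, median, quartiles and range, so a control row resting on one or two patients, or an outlying systemic level, would show. SAP 15.5.2 lists each level, and SAP 13 summarises concomitant medication. A reader could match the two by hand.
- **Pooling of the two drugs is not shown.** Protocol 15.2.5.3 summarises laboratory results by parameter, and the table shells are not available.
- **The table's purpose is inferred.** It sits under clinical laboratory data, includes mTOR inhibitors, and also fits routine drug monitoring. The open-label argument in Protocol 9.2 rests on earlier data, and also on an objective endpoint, blinded technicians and blinded central reading.
- **Little depends on it.** SAP 15.1 plans no inference on safety endpoints.

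All of this stands and limits the weight of the point. It does not remove it: the protocol names a comparison of means, switching is permitted, and no planned table separates the two sources.

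**Conclusion.** The point holds as a gap in a descriptive safety table. The planned CsA means combine two sources of exposure, and a small imbalance in switching can distort or reverse the arm comparison. On the assumed levels, reversal needs an excess of about 1 to 17 switched SoC patients of 84, or a single one if control patients are assayed only while on CsA. The true size depends on switch counts, levels and assay practice, none of which the documents give. The primary analysis and the type I error are unaffected.

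A reader might infer three stronger conclusions that the documents do not support:
- **That the table mainly reflects who was switched.** This needs enough switches. At an inhaled trough of 5 and a systemic trough of 150 ng/mL, one or two leave most of the L-CsA mean to inhalation.
- **That the SoC mean must be a systemic-dosing level.** This is true only if unswitched control patients are not assayed.
- **That change from baseline in CsA is undefined for most patients.** This is true only if CsA is not assayed at baseline. Blood sampling is scheduled at Screening and Visit 1, and the documents do not say whether CsA is measured then in patients on tacrolimus.

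**What to change.** Amend SAP 15.5.2, before results by arm are seen, as follows:

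1. Tabulate CsA and tacrolimus separately.
2. Show CsA by arm and visit in two groups: samples with no systemic CsA up to that sample, and samples on or after systemic CsA. Define the groups from concomitant-medication dates, drug codes and routes. The route matters because Protocol 11.3.4 allows topical CsA such as eye drops.
3. Give the number assayed for CsA in each cell and the number switched per arm.
4. Base any statement on systemic exposure from inhaled L-CsA on observed levels in the samples without systemic CsA.
5. State how unassayed values and values below the assay limit are handled.

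Protocol 15 makes the final SAP the analysis of record where the two differ, so a SAP change is enough. The cost is a few sentences, one derived flag and smaller cells. Start and stop dates (Protocol 11.3.1) and the coding and route rules (SAP 12) already supply what is needed. No new samples are required, and patient management does not change.
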